15.8.2 Primary Safety Endpoint

The primary safety events are listed in Section 8.2. Patients who experience any of these events will be counted as safety failures in the analysis. Detailed summaries of reported events will be provided, including calculated rates of events and corresponding 95% confidence intervals. The following hypothesis test will be evaluated under a one-sample, one-sided exact binomial test at the 0.025 significance level:

H_o: $P_{Vici} \le 0.94$ H_A: $P_{Vici} > 0.94$,

STE-HUM-007P US Clinical Protocol Revision C

Confidential

Page 46 of 70

where P_{Vici} is the freedom from event rate of pre-specified safety events associated with use of the Veniti Vici Venous Stent System and 0.94 is the pre-specified performance goal.

15.8.3 Secondary Efficacy Endpoint

In order to control the overall type I error rate, the formal secondary efficacy endpoint will only be assessed if the primary endpoint objective is met. The secondary efficacy endpoint is a binary response variable based on achieving at least 50% improvement in VCSS. The following hypothesis test will be evaluated under a one-sample, one-sided exact binomial test at the 0.025 significance level:

H₀: P_{Vici} ≤ 0.50

 $H_A: P_{Vici} > 0.50,$

where $\mathsf{P}_{\mathsf{Vici}}$ is the VCSS success rate, and 0.50 is the pre-specified performance goal.

15.9 Evaluation of Ancillary Endpoints

General Considerations

None of the evaluations of ancillary endpoints will include hypothesis tests. Instead, the mean or proportion of each will be estimated along with the 95% confidence interval (CI). Only the PP analysis will be performed on secondary endpoints (i.e., patients or limbs who contribute data will be included; those without data on a particular endpoint will be ignored).

15.9.1 Procedural Endpoints

Procedural technical success. The proportion of limbs with procedural technical success and the 95% CI will be reported.

Lesion success. The proportion of limbs with lesion success and the 95% CI will be reported.

Procedural success. The proportion of limbs with procedural success and the 95% CI will be reported.

Late technical success. The proportion of limbs with late technical success and the 95% CI will be reported.

Subgroup analysis. A subgroup analysis will be performed to evaluate device performance across genders.

15.9.2 Clinical Endpoints

Change in Venous Clinical Severity Scoring System (VCSS). Each limb's change VCSS will be calculated; the mean of the changes and its 95% CI will be reported.

Change in Quality of Life (CIVIQ-2). Each patient's area under the curve (AUC) will be calculated for the CIVIQ-2; the mean AUC and its 95% CI will be reported.

STE-HUM-007P US Clinical Protocol Revision C

Confidential

Page 47 of 70

Minor outcomes. The proportion of patients with minor outcomes and the 95% CI will be reported.

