STE-HUM-007P US Clinical Protocol Revision C

Confidential

Page 23 of 70

- ii. Kinking, defined as >50% diameter reduction of the stent with the stent doubling or bending on itself
- iii. Recoil, defined a poor radial resistance to diffuse collapse, which results in >50% diameter reduction of the stent (i.e., stent diameters obtained throughout the study period as compared to the final stent diameter after insertion measured by DUS or venogram).
- Absence of fractures, which will be assessed as per Jaff, et al.1 (See Appendix 3.) Data to be collected for each fracture identified includes:

Limb (right or left) Venous segment(s) where fractures are located Overlapping versus non-overlapping Type of fracture (Type I, II, III, IV)

5. Subgroup analysis to evaluate device performance across genders.

Clinical Endpoints

- 6. Improvement in Venous Clinical Severity Scoring (VCSS) at 6 and 12 months
- 7. Improvements in Quality of Life (CIVIQ-2) at 12 months (See Appendix 5.)
- 8. Minor outcomes: complications occurring within 30 days of the procedure that do not meet the definition of an MAE, do not require hospitalization and do not delay discharge.

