9.3 Baseline Evaluation (within 30 days of implant procedure)

Patients who sign an informed consent will undergo baseline testing:

- History and physical examination
- Laboratory evaluation (CBC and eGFR will be required for all patients; Patients on a Vitamin K antagonist or direct thrombin or Factor Xa inhibitors, prior to the intervention, require a PT with INR; subjects on heparin prior to the intervention require an aPTT. Patients with history of liver disease will require a PT with INR and an aPTT.)
- Medication review
- Pregnancy test in females of child-bearing age (within 48 hours of implant procedure)
- CEAP Assessment (See Appendix 4.)
- CIVIQ-2 Quality of Life questionnaire (See Appendix 5.)
- VAS pain score (See Appendix 6.)
- VCSS (See Appendix 7.)

9.4 **Pre-Procedural Evaluation**

Patients who consent, and who meet the pre-procedural inclusion and exclusion criteria, will undergo baseline venography to verify appropriateness for enrollment, as determined by the treating physician.

- Venography only to ascertain obstruction with at least a ≥50% in the target vessel lumen diameter compared to the normal vein lumen diameter immediately peripheral to the target lesion as measured by venogram. IVUS may not be used to fulfill this requirement.
- Absence of obstruction extending into the inferior vena cava (IVC) as determined by any imaging modality.

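### The quality-of-life outcome is improvement in CIVIQ-2 at 12 months, but the only CIVIQ-2 statistic specified is a mean AUC, which does not estimate that improvement

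*Combined protocol and SAP*

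**What the plan says.** Section 7.4 lists, among the clinical ancillary outcomes, "Improvements in Quality of Life (CIVIQ-2) at 12 months". The item just before it, on VCSS, names both 6 and 12 months, so the single time point for CIVIQ-2 looks deliberate.

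The questionnaire is scheduled at baseline (9.3), 6 months (9.8) and 12 months (9.9), and the table in section 10 agrees.

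The CIVIQ-2 entry in 15.9.2 is labelled as a change in quality of life, but the calculation it gives is that each patient's "area under the curve (AUC) will be calculated for the CIVIQ-2; the mean AUC and its 95% CI will be reported". It states no baseline subtraction, time limits, interpolation rule, scaling or reference value. The VCSS entry directly above is handled differently: "Each limb's change VCSS will be calculated; the mean of the changes and its 95% CI will be reported".

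Section 15.9 adds two general rules. The first is "None of the evaluations of ancillary endpoints will include hypothesis tests"; each ancillary endpoint instead gets an estimated mean or proportion with a 95% CI. The second concerns missing data: "those without data on a particular endpoint will be ignored".

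**The concern.** An improvement at 12 months is a difference between two scores. An AUC of the raw score is a level averaged over the year. The baseline score enters it with the same sign as the 12-month score, so a group that gets better and a group that gets worse can report the same mean. The trial has a single arm and sets no CIVIQ-2 reference value, so nothing is available against which a mean AUC could be read as improvement.

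If the plan is followed as written, it yields no estimate of its own named quality-of-life outcome. A 12-month change reported in its place would be an analysis that 15.9.2 does not specify.

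**Working it through.** The documents give no sample size, SD or expected effect for CIVIQ-2, so there is no figure of the plan's to reproduce. The check is algebraic.

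**Inputs.**
- Visits at baseline, 6 and 12 months (9.3, 9.8, 9.9), taken at their nominal times.
- Assumed, because the plan is silent: trapezoidal rule, baseline included, AUC divided by the one-year span.
- Illustrative scores on an assumed raw sum of 20 to 100 (Appendix 5 has 20 items scored 1 to 5, higher being worse, and states no total-score rule). These are not estimates for this trial.

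Write b, m6 and m12 for the three scores, d6 = m6 - b and d12 = m12 - b. The outcome in 7.4 is d12. The AUC is linear in the scores, so with complete data the mean of the patients' AUCs equals the AUC of the group means, and the weights below hold under any scoring rule.

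**Reading 1: AUC of the score, as literally written.**

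AUC = 0.5 × (b + m6)/2 + 0.5 × (m6 + m12)/2 = 0.25b + 0.50m6 + 0.25m12

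| Path (0/6/12 months) | AUC | 12-month change |
|---|---|---|
| 60/50/40 | 15 + 25 + 10 = 50.0 | -20 |
| 50/50/50 | 12.5 + 25 + 12.5 = 50.0 | 0 |
| 40/50/60 | 10 + 25 + 15 = 50.0 | +20 |

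Swapping b and m12 leaves the AUC unchanged. Two stable groups, 50/50/50 and 60/60/60, differ (50.0 against 60.0) although neither changed.

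**Reading 2: AUC of change from baseline, as the entry's label may intend.**

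AUC of change = AUC - b = 0.5·d6 + 0.25·d12

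| Path | AUC of change | 12-month change |
|---|---|---|
| 60/40/40 (sustained, d6 = d12) | -10 - 5 = -15.0 (0.75 of d12) | -20 |
| 60/50/40 (linear, d6 = d12/2) | -5 - 5 = -10.0 (0.50 of d12) | -20 |
| 60/40/60 (benefit lost) | -10 + 0 = -10.0 | 0 |
| 60/60/20 (late benefit) | 0 - 10 = -10.0 | -40 |
| 60/40/70 (relapse) | -10 + 2.5 = -7.5 | +10 |

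This reading recovers the average direction over the year. The same value of -10.0 nevertheless goes with 12-month changes of -20, 0 and -40.

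**Visit timing.** With actual visit days t6 and t12, the weight on d6 relative to d12 is t12/(t12 - t6). Across the allowed windows (180 ± 30 and 365 ± 60 days) it runs from 425/(425 - 150) = 1.5 to 305/(305 - 210) = 3.2. If the AUC is not divided by follow-up time, a constant score of 50 gives anything from 50 × 305 = 15,250 to 50 × 425 = 21,250 score-days.

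**The case against.** The strongest reply is that the entry in 15.9.2 is labelled as a change, in parallel with the VCSS entry, so the AUC was meant to summarise change and the literal reading is uncharitable. That is plausible. It removes the conclusion that the statistic cannot show improvement at all, but the second table shows that the 12-month change is still not what is estimated.

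The general rule in 15.9, a mean or proportion with a CI for each ancillary endpoint, could be read as already covering the mean 12-month improvement. It names no CIVIQ-2 change score, however, and the sentence specific to this endpoint says that the mean is of AUCs. This softens the point without answering it.

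The 2:1 weighting does depend on assumed visit times and on the trapezoidal rule. The weight moves with the visit days, but at no point in the allowed windows does the weighted sum become the 12-month change alone.

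An AUC is also a legitimate summary of burden over a year. That is a different quantity from the one 7.4 names.

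One caution about the remedy stands. Section 9.10 does not require further assessment of secondary endpoints in patients who fail the efficacy endpoint before 12 months. If that covers CIVIQ-2, a change computed only in patients with both scores may omit failed stents and flatter the device. The AUC, which also uses the 12-month score, would be affected at least as much.

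**Conclusion.** The concern holds. The statistic in 15.9.2 does not estimate the outcome in 7.4 under either reading. Taken literally it cannot distinguish improvement from its mirror-image worsening. Taken as an AUC of change, it gives 0.75 of a sustained 12-month change and 0.50 of a linear one, and it can be non-zero or of opposite sign when the 12-month change is zero or reversed. These multiples assume a trapezoidal AUC scaled to one year with visits at 0, 6 and 12 months. The mismatch itself does not depend on the scoring rule or on the visit day within its window.

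The importance is low. The endpoint is ancillary, carries no hypothesis test and has no role in trial success, and the scores needed for the correct summary are already collected. It is worth correcting because the plan as written gives the wrong quantity for a named outcome.

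**What to change.** Replace the CIVIQ-2 sentence in 15.9.2 with wording such as: *For every patient with a CIVIQ-2 score at both baseline and 12 months, the 12-month score minus the baseline score will be computed. The mean difference will be presented with a 95% CI, together with the number of patients lacking either score.* This brings CIVIQ-2 into line with the treatment of VCSS and with the available-data rule in 15.9. Given section 9.10, it would help to say how many of the patients without a 12-month score had an earlier patency failure.

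If the AUC is kept, label it supplementary, compute it on change from baseline, state its time limits and scaling, and say whether two of the three visits are enough, which the rule in 15.9 does not settle.

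The cost is one sentence. No visit, questionnaire or data field is added.

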16 CORE LAB ASSESSMENTS

16.1 Venogram Core Laboratory

A copy of all venographic studies collected in the study will be sent to the angiographic core laboratory for review. Venographic site assessment guidelines and shipping requirements will be provided by angiographic core lab (e.g., during the site training).

16.2 Duplex Ultrasound Core Laboratory

All duplex ultrasound examinations collected through the 36 month follow-up of the study will be sent to the duplex ultrasound core laboratory for review and assessment. Duplex assessment guidelines, technician training (if required), and data submitting guidelines will be provided by the duplex ultrasound core laboratory (e.g., during the site training).

Pre-enrollment DUS is considered an investigator-determined inclusion criterion, and does not require Core Laboratory confirmation.

16.3 IVUS Core Laboratory

All IVUS evaluations will be analyzed by the independent core laboratory.

17 INSTRUCTIONS FOR USE

See the Instructions for the Veniti Vici Venous Stent System.

18 INVESTIGATOR TRAINING

Investigators responsible for delivering the Veniti Vici Venous Stent will receive sufficient training to ensure competence in the execution of all aspects of the procedures required to deliver the Veniti Vici Venous Stent. Training may include hands on experience with demonstration devices, didactic presentations, or observing placement procedures performed by another physician and will include an extensive review of this study protocol and the Veniti Vici Venous Stent System Instructions for Use.

19 MONITORING PROCEDURES

19.1 Site Monitoring Plan

It is the responsibility of Veniti to ensure that proper monitoring of the investigation is conducted and that IRB/EC review and approval of the investigation is obtained. Monitoring visits will occur based on enrollment at the site, and at least annually. Adequately trained Veniti personnel or delegates appointed by the study sponsor will monitor in order to ensure that the investigation is conducted, recorded and reported in accordance with:

• The signed Investigator Responsibility Agreement

STE-HUM-007P US Clinical Protocol Revision C

- The Investigational Plan
- Applicable laws and regulations
- Any requirements imposed by Veniti

All monitoring activities will be performed and/or supervised by the overall study manager, [name], MS, Senior Director of Clinical Affairs, Veniti. Monitoring will be planned periodically at the study site to assure compliance with the study protocol. The sponsor (or an appropriate designee) must therefore be allowed access to the patients' files as per the informed consent at the investigator's site when so requested. The monitoring visits may include but are not limited to the following:

19.2 Site Initiation Visit

Site Initiation visits will be conducted by Veniti personnel or delegates. The Veniti personnel or delegates will be responsible for the training of the investigators and other personnel. The Veniti personnel or delegates will review all documentation collected from the site and ensure that each site has met the regulatory requirements and has all the necessary documentation and training to begin the clinical study and assures that the Investigator/staff:

- Understands the investigational status of the device;
- Understands the Investigational Plan including the protocol, records and reports (as specified in section F);
- Understands the requirements for conducting a clinical study on medical devices;
- Submits the Investigational Plan and required supporting documentation to the study center's Institutional Review Board (IRB) or Ethics Committee (EC) for their review/approval;
- Submits all FDA and annual reports to their IRB/EC;
- Maintains all correspondence, the Investigational Plan, and all required records on file, and submits required reports in due time;
- Assumes responsibility for the investigation at his/her institution which may include supervision of some tasks.

19.3 Routine Monitoring

Routine monitoring visits are made periodically to assess the investigator's adherence to the Investigational Plan, IRB/EC review of study progress (if appropriate), maintenance of records and reports, continued acceptability of the facilities, and selected review of source documents to assess accuracy, completeness, legibility and omissions to the Case Report Forms. The monitors will acquire information to assess the progress of the study (toward meeting study objectives) and identify any concerns that stem from observation of device performance and/or review of the investigator's patient records, study management documents, device tracking and patient informed consent documents. Resolution of concerns and completion of assigned tasks may be documented by the monitors. Review of any ongoing findings may occur during monitoring visits.

STE-HUM-007P US Clinical Protocol Revision C

Confidential

Page 49 of 70

19.4 **Closeout Visit**

Veniti personnel or delegates will schedule and conduct a Site Closeout Visit upon study or site closure. If the site has not enrolled any subjects in the study, the closeout visit can be done via phone. All investigational product will be returned to Veniti at the time of the closeout.

20 INSTITUTIONAL REVIEW BOARD/ETHICS COMMITTEE (IRB/EC)

The protocol, informed consent document, and relevant supporting information must be submitted to the IRB for review and must be approved before the study is initiated. In addition, any subject recruitment materials must be approved by the IRB/EC prior to use. This study will be conducted in accordance with the ethical principles that have their origin in the Declaration of Helsinki and that are consistent with Good Clinical Practice, ISO 14155-2011, and applicable regulatory requirements. The study must be conducted in accordance with the regulations of the United Stated Food and Drug Administration (FDA) as described in 21 CFR 50 and 56, applicable laws and the IRB requirements.

The sponsor must submit any change to the protocol to the IRB for review and approval before implementation. A protocol change intended to eliminate an apparent immediate hazard to subjects may be implemented immediately, provided the FDA and the reviewing IRB are notified within 5 working days.

It is the responsibility of the investigator to provide each subject with full and adequate verbal and written information, before inclusion in the study, using the IRB approved informed consent document, including the objective and procedures of the study and the possible risks involved. Informed consent must be obtained prior to performing any study-related procedures, including screening and changes in medications including any washout of medications. A copy of the signed informed consent document must be given to the study subject.

The investigators have been selected because of their medical qualifications, interest in participation, ability to conduct and document the results of the study, ability to accrue patients.

All investigators will provide their curriculum vitae to Veniti, Inc. and sign a Financial Disclosure and Investigator Agreement.

21 SUBJECTS' CONFIDENTIALITY

Information about study subjects will be kept confidential and managed according to the requirements of the Health Insurance Portability and Accountability Act of 1996 (HIPAA). The HIPAA regulations require a signed subject authorization informing the subject of the following:

- What protected health information (PHI) will be collected from subjects in this study •
- Who will have access to that information
- Who will use or disclose that information
- The rights of a research subject to revoke their authorization for use of their PHI.

STE-HUM-007P US Clinical Protocol Revision C

In the event that a subject revokes authorization to collect or use PHI, the Investigator retains the ability to use all information collected prior to the revocation of subject authorization. For subjects that have revoked authorization to collect or use PHI, attempts should be made to obtain permission to collect at least vital status (i.e., fact whether the subject is alive) at the end of their scheduled study period.

All data used in the analysis and summary of this study will be anonymous. Access to subject files will be limited to authorized personnel involved in the study.

At time of enrollment, subjects will be assigned a trial-specific number identifier. This identifier will be used throughout the course of the study (instead of patient name, hospital ID, etc.) to ensure subjects confidentiality.

22 PUBLICATIONS

At the conclusion of all follow-up visits, a multi-site abstract reporting the preliminary results may be prepared and presented at a major endovascular meeting. A complete multi-center trial manuscript is the primary publication for the study. The publication of results from any single-site experience within the study must not be submitted for publication or presentation until a multi-center manuscript is published, unless otherwise approved by the Sponsor.

The Sponsor will establish a publication committee and policy. The committee membership may include the overall Principal Investigator, other investigators from the study, and representatives of Veniti (e.g. statistician, clinical research specialist, etc.). The committee will establish a publication strategy. The committee will be responsible for overseeing the development of any multi-site study manuscripts or abstracts. Any multi-site publications of study data must be reviewed and approved by at least two physician members of the publication committee prior to submission. Any previously unpublished information provided to the investigators by Veniti, such as patent applications, manufacturing processes and basic scientific data, is considered confidential and will remain the sole property of Veniti. The investigator agrees to use this information only in accomplishing this study and will not use it for other purposes without Veniti's written consent.

In addition, all multi-site and single-site abstracts or manuscripts must be reviewed by Veniti prior to submission. Veniti will limit its review to a determination of whether or not confidential information is disclosed, and will not attempt to censor the data or conclusions made in the publication.

23 DATA MANAGEMENT

An electronic database capture (EDC) system (Mednet, Minneapolis, MN) will be used to record all subjects' data in the study. This secure EDC will be backed up regularly to ensure collected data storage. The server will be accessible by password for all approved users via the internet, and data analytical workstations will be used for data processing and management.

Conventional data verification sub-routines will be extensively programmed to test entry and logical errors, while all individual (subject-based) eCRFs will be linked for

STE-HUM-007P US Clinical Protocol Revision C

cross-reference. Periodic analysis of each data field (across subjects) will be performed in order to examine the expected distributions of data, and to identify outliers for possible data mistakes. Corrections to data mistakes will be requested via queries.

All information and data concerning subjects or their participation in this study will be considered confidential. Only authorized personnel involved in the study will have access to these confidential files. As described in Section 21, each subject will be assigned unique identifier; therefore, all data used in the analysis and reporting of this evaluation will be without identifiable reference to the subject.

